The assumption made in arriving at this sample size is that ultrasound achieves an accurate and complete diagnosis of a developmental brain abnormality in around 70% of cases [44-58], and with the addition of in utero MR, this figure would rise to at least 80%. If the "true" increase is just 10%, then a sample size of 336 would mean we can be sure of detecting an improvement in diagnostic accuracy with 90% power and 95% confidence. We believe that a change of this magnitude would be of clinical importance, as it could very well lead to changes in fetal prognosis and management intent in around 5% of all cases. The proposed sample size is sufficient to detect such changes in these important secondary outcome measures.

We will recruit from at least 13 fetal medicine units in England and Scotland, many of which have previously collaborated with the Sheffield in utero MR group. These centres cover a potential referral base of approximately 298,000 deliveries annually, this being around 40% of all deliveries in Great Britain. The incidence of developmental brain abnormalities detected by second trimester ultrasound screening, and therefore potentially eligible for inclusion in the study, is estimated at 3 per 1,000 deliveries [54, 58-60]. In order to recruit the required total of 750 cases, and allowing for a failure/refusal to recruit 50-60% of these eligible cases, the study will need to recruit for twenty two months.

Losses to follow-up during the study are estimated at just 10%. This figure reflects the nature of the study, as we are dealing with relatively young, healthy adults who have expressed a wish to gather more information about their pregnancy. The rate of incomplete cases, i.e. those where an outcome reference diagnosis is not achieved, is estimated at

around 20%. In support of this estimate, data from a tertiary fetal medicine department within our group indicates that their completion rate for autopsy following termination of pregnancy for fetal ventriculomegaly is 83% [58]. Allowance is also made for a small number (4%) of cancelled, abandoned or incomplete MR examinations. See Figure 3 below for estimated recruitment numbers and drop out rate at each stage of the study.

Figure 3 – Recruitment & Drop Out Estimates

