Appendix

Add-on study

Introduction

There are two elements to this add-on study to MERIDIAN, both of which have been supported by the NIHR-HTA. The first relates to the need to describe the False Negative Rate of ultrasonography as performed by an experienced feto-maternal expert (study A₁). Recruitment into MERIDIAN includes only fetuses thought to have brain abnormalities on ultrasound so the false negative rate cannot be estimated by the main MERIDIAN study. The second study will calculate the rate of unexpected brain abnormalities (i.e. not shown on ultrasonography) in fetuses with non-CNS abnormalities (Study A₂). The results of both studies will be of great potential importance to the NHS.

In both studies we plan to recruit 200 women whose fetus has had a detailed anomaly ultrasound by a feto-maternal expert which showed no brain abnormality. If a woman has had a previous pregnancy complicated by a brain abnormality the women will not be invited into the study. If participant numbers are not sufficient from this group we intend to recruit pregnant women from the general population who have not had a detailed anomaly ultrasound and arrange a fetal brain ultrasound with a fetal medicine consultant as part of the study.

Aims and Objectives

Study A₁

The aim is to answer the question:

What is the false negative rate of ante-natal ultrasound performed by feto-maternal experts when trying to detect fetal brain abnormalities?

Study A₂

[figure not shown]
The aim is to answer the question:

What is the rate of unexpected brain abnormalities detected by iuMR imaging in fetuses with known non-CNS abnormalities.

Study Design

Participants will be recruited via option 1. Option 2 will be held in reserve and only used if recruitment via option 1 is insufficient.

Participant pathway diagram Option 1:

Participant pathway diagram Option 2:

Initial identification of participant

- Pregnant women whose pregnancy is normal are sought through:
 - Scanning ultrasound clinics at participating MERIDIAN sites
 - Charitable organisations working in pregnancy, working within the Sheffield area
 - Community midwives in Sheffield area
 - GP lists in Sheffield area
 - Local media
- Participants are given a patient information leaflet and or information sheet and details of how to register their interest in taking part in the study (phone/email)

Screening (telephone call with participant)

- Department of academic radiology has contact with participant

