- If participant is still interested in the study they will be asked screening questions
- Date for Ultrasound and MRI scan arranged
- Full patient information sheet sent to participant (if not already received)

Detailed Ultrasound & MRI visit (visit to academic Unit of radiology in Sheffield)

- Participant visits academic of radiology department,
- consent taken, including permission for scan results to be sent to GP
- Brain ultrasound performed
- MRI scan performed
- Participant offered MR image of baby to keep and £10 voucher.

Post MRI activities (no participant contact required)

- Results of Ultrasound & MRI scan sent to GP

Inclusion Exclusion Criteria

Inclusion Criteria

A participant is eligible for the trial if the following criteria are met:

For study A1

1. Has an ongoing singleton or multi-fetal pregnancy of at least 18⁺⁰ weeks gestation* by ultrasound dating.
2. Is thought to be carrying a fetus with no abnormality whatsoever (i.e. no brain or somatic abnormality) **

For study A2

1. Has an ongoing singleton or multi-fetal pregnancy of at least 18⁺⁰ weeks gestation* by ultrasound dating.
2. Is thought to be carrying a fetus with no brain abnormality but does have a confirmed somatic abnormality **

* It is a requirement that MR scans are not carried out prior to 18 weeks gestation. Women can be consented at 17 weeks gestation where there is a continuing pregnancy and they will be 18 weeks at the time of the MR examination.

** if recruited via option 1 this criterion will be based on a normal mid pregnancy anomaly scan in a fetal medicine centre. If recruited via option 2 this will be self-reported by the participant based on their medical care to date e.g. screening ultrasound

Exclusion Criteria

A participant is excluded from the trial if any of the following criteria are met:

1. Has a past history of a fetal brain anomaly in a previous pregnancy
2. Inability to give informed consent.
3. Has a cardiac pacemaker, intra-orbital metallic foreign body, or recent surgery with metallic sutures or implant.
4. Has previously experienced or is likely to suffer severe anxiety or claustrophobia in relation to MR imaging examination.
5. Is unable or unwilling to travel to Sheffield or attend St George's Hospital for specialist MR imaging.

6. Is unable to understand English (except where satisfactory translation services are available).
7. Is under the age of 16 years.

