would be take place within one week of the ultrasound, but participants will still be accepted regardless of the interval between ultrasound and MRI.

Study Visit (option 1 pathway)

Participants will attend a clinic at the academic unit of radiology or St George's Hospital. Informed consent will be taken.

After consent background information about the participant will be recorded by staff.

The participant will have the MRI scan and be offered an image of the baby to keep. Participants will also be offered a £10 voucher . Normally the participants will be able to have a discussion about the results of the scan and be given some immediate feedback, the participants will be reminded that results are going to be sent to their GP.

No further patient contact is required after this visit.

Post Visit activities (option 1 pathway)

After the visit a copy of the MRI report will be sent to the participant's GP and their consultant if they are still receiving care from a fetal medicine unit.

A copy of the detailed anomaly ultrasound report will be requested from the referring MERIDIAN centre (unless the participant had a copy in their hand held maternity notes, if this is the case a copy of the report from the maternity notes will be used).

Assessments and procedures (option 2 pathway)

Enrolment (option 2 pathway)

Participating MERIDIAN sites will be able to identify participants as for option 1, but to a wider group of patients who have not had an ultrasound by a fetal medicine consultant.

In addition suitable organisations working in Sheffield and surrounding areas such as Charitable organisations working in pregnancy, Community midwives, GPs will be approached and asked if they will make information about the study available to pregnant women they work with. Potential participants will have access to participant flyer and full information sheet. The participant flyer will have phone and email contact details for Academic Unit of radiology and participants can register their interest.

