Only adverse events that occur during the MRI scan will be captured. There will be no participant follow up as part of this study.

The reports of scans performed for this study will be sent to the participant's doctor(s), in some cases this will be a GP in other cases a consultant. If an anomaly is detected it will be the doctor's responsibility as part of his or her normal clinical care to take appropriate action.

Statistics

Starting from the assumption that no US false negatives will be found, the extension study will recruit 200 fetuses in each group. This figure has been derived from the $3/n$ rule (Eypasch et al., 1995), a large sample approximation of the upper 95% confidence interval for very rare events. If no adverse events are observed in a sample of size of n , this does not

imply that adverse events are impossible; instead, a confidence interval can be constructed to quantify the upper limit of the event rate. The study will therefore estimate the negative predictive value of US to an upper limit of 3/200 or 1.5% in the absence of false negatives. If false positives are encountered, the study will estimate the negative predictive value to a standard error of $\leq 2\%$ for plausible occurrence rates (i.e. $<10\%$).

Reference

MERIDIAN – 2-3 year follow up study

Funded by the National Institute for Health Research's Health Technology Assessment programme (project number 09-06-01)

Magnetic resonance imaging to enhance the diagnosis of fetal developmental brain abnormalities in utero - 2-3 year follow up study

[name]
Academic Unit of Radiology
University of Sheffield
[name]
Royal Hallamshire Hospital
Sheffield
[name]

[name] (tel)
[name] (fax)

[contact]

www.shef.ac.uk/meridian

RESEARCH PROTOCOL
(Version 4.0) 28th September 2016

Sheffield CTRU ref	URMS 144460
CSP	180504
STH R&D ref	STH19125
NIHR HTA ref	09-06-01
Ethics ref	15-YH-0398
ISRCTN	ISRCTN27626961

Authorised by: [name]

Magnetic resonance imaging to enhance the diagnosis of fetal developmental brain abnormalities in utero – 2-3 year follow up study

MERIDIAN

Contents

Study Summary.....	6
1. Introduction.....	7
2. Aims and objectives	8
3. Study Design.....	9
4. Selection and withdrawal of participants	11
5. Enrolment.....	12
6. Assessments and procedures.....	13
7. Statistics	19

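### Add-on study A1 sets out to estimate the false negative rate of expert ultrasound but enrols only ultrasound-negative fetuses, so it can estimate only 1 − NPV; its Statistics text also mislabels the figures

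*Protocol*

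**What the plan says.** The Appendix (Add-on study, Introduction) explains that the main study takes only fetuses with a suspected brain abnormality on ultrasound, "so the false negative rate cannot be estimated by the main MERIDIAN study". A1 is meant to fill that gap, and its aim (Aims and Objectives, Study A1) is to answer "What is the false negative rate of ante-natal ultrasound performed by feto-maternal experts when trying to detect fetal brain abnormalities".

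The add-on plans to "recruit 200 women whose fetus has had a detailed anomaly ultrasound by a feto-maternal expert which showed no brain abnormality" in each of its two studies. The A1 inclusion criteria repeat the restriction: the fetus must be thought to have no brain or somatic abnormality. Under option 2 the ultrasound is done at the study visit, and a woman whose scan suggests a brain abnormality leaves data collection.

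The add-on Statistics section assumes no false negatives, applies the 3/n rule, and says the study will "estimate the negative predictive value of US to an upper limit of 3/200 or 1.5" per cent. It then says that, if false positives are met, the standard error will be at most 2% for rates below 10%.

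On verification, the Safety section says "There will be no participant follow up as part of this study". On timing, the option 1 enrolment text gives one week as the ideal but adds that "participants will still be accepted regardless of the interval between ultrasound and MRI".

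**The concern.** A false negative rate is the share of abnormal fetuses that ultrasound misses, so its denominator is all abnormal fetuses, detected and missed. A sample selected on a negative ultrasound contains no detected cases and so lacks that denominator. It gives the share of ultrasound-negative fetuses that are abnormal, which is a different quantity and is small whenever abnormality is rare, however poor the test.

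The introduction sees this problem in the main study, which has only ultrasound positives, but not its mirror image in A1, which has only ultrasound negatives. The aim and the Statistics section then name different quantities.

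What is at stake is how the planned-for result is read. Zero abnormalities in 200, set against the stated aim, would read as a false negative rate below 1.5%, that is, a sensitivity above 98.5%. The design cannot support that.

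**Working it through.** **1. The plan's own figure.** Inputs from the add-on Statistics section: n = 200 per group, zero events, 95% level, 3/n rule.

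- 3/n = 3/200 = 1.5%, as stated.
- Exact one-sided 95% limit: 1 − 0.05^(1/200) = 1.49%. The approximation is sound. (The exact two-sided limit is 1 − 0.025^(1/200) = 1.83%.)

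The count being bounded is missed abnormalities and the denominator is ultrasound-negative fetuses. So 1.5% is the upper limit of 1 − NPV, and the matching statement for NPV is a lower limit of 100% − 1.5% = 98.5%.

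**2. What the design can identify.**

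- False negative rate = FN / (FN + TP)
- 1 − NPV = FN / (FN + TN)

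A1 fills only the FN and TN cells. TP is empty by selection, so the first ratio cannot be formed. FP is empty too, so an ultrasound false positive cannot occur in this sample; the sentence about false positives must mean false negatives.

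**3. What zero in 200 implies for the false negative rate.** Let u be the upper limit of 1 − NPV, d the ultrasound-positive share of the source population, and PPV the share of ultrasound positives that are true. Then

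upper limit of false negative rate = u(1 − d) / [u(1 − d) + d × PPV]

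with u = 0.015. The add-on gives neither d nor PPV. I assume PPV = 1 and show a range for d. The value 0.003 is borrowed from the main protocol (section 9, Sample size), where the incidence of abnormalities detected by second-trimester screening is "estimated at 3 per 1,000 deliveries".

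| d | missed, u(1 − d) | detected, d | upper limit |
|---|---|---|---|
| 0.1% | 0.014985 | 0.001 | 94% |
| 0.3% | 0.014955 | 0.003 | 83% |
| 1% | 0.01485 | 0.01 | 60% |
| 5% | 0.01425 | 0.05 | 22% |
| 10% | 0.0135 | 0.10 | 12% |

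A lower PPV raises these limits: at PPV = 0.7, also an assumption, the 0.3% row becomes 88% and the 10% row 16%.

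**4. How easily zero events could arise.** Take d = 0.003, PPV = 1, and suppose ultrasound misses half of all abnormalities. Missed cases then equal detected cases, so the rate among ultrasound negatives is 0.003/0.997 = 0.00301. The chance of zero in 200 is (1 − 0.00301)^200 = 55%.

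**5. The standard error.** At a rate of 10%, √(0.10 × 0.90 / 200) = 2.12%. For a standard error of 2%, p(1 − p) = 0.0004 × 200 = 0.08, so p = [1 − √(1 − 0.32)]/2 = 8.8%. The claim holds to about 8.8%, not to 10%.

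**The case against.** The Statistics section already names the negative predictive value, and the sample size, the 3/n rule and the precision statement are all built on it. On this view the aim is loosely worded and the analysis is right. That is partly fair: the 200 per group is sensible for 1 − NPV, and nothing in enrolment or procedures has to change. But the phrase in the aim is the formal research question and the reason given for doing A1, so the mismatch stands.

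A reader might infer three stronger things, which the documents do not support.

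- *That the result would be compatible with ultrasound missing 83% of abnormalities, as a finding in itself.* That figure is an upper limit, not an expected value. It borrows a screening incidence the add-on never uses and treats every ultrasound positive as true. Option 1 draws on women scanned in fetal medicine centres, whose ultrasound-positive share is not given, and A1 excludes somatic abnormality and a previous affected pregnancy. Only the range is defensible. It stays well above 1.5% throughout.
- *That the result will be reported as a low false negative rate.* Nothing says how it will be reported, and the Statistics section points to NPV.
- *That the open ultrasound-to-MR interval undermines the estimate.* Enrolment aims for the earliest appointment, posted invitations go to women scanned in the last seven days, one week is the ideal, and option 2 does both scans at one visit. Some later findings in option 1 could still be charged to ultrasound, but this does not call for a restricted main analysis.

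The slips in the Statistics text are editorial, and the standard error did not drive the sample size.

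**Conclusion.** The point holds. That A1 cannot estimate the false negative rate follows from its selection rule and needs no outside figure. What it can give is the rate of MR-reported abnormality among expert-ultrasound-negative fetuses, with MR itself unverified, so MR errors in either direction pass into the estimate. Zero in 200 would support an upper 95% limit of 1.5% for that rate. For the share of abnormalities missed, the corresponding limit runs from about 94% to 12% as the ultrasound-positive share goes from 0.1% to 10%, assuming all ultrasound positives are true.

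The three statements in the add-on Statistics section are wrong as written, the standard error only slightly. This should be fixed, but it concerns a descriptive add-on and does not touch the main study's primary outcomes, hypothesis or sample size.

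**What to change.** 1. Restate the A1 aim as the rate of brain abnormality reported on in utero MR in fetuses judged normal by expert ultrasound (1 − NPV, with MR as an unverified comparator).
2. State that the false negative rate is not estimable from A1, or give it only as a bound over a stated range of ultrasound-positive share or prevalence, with the assumption about true positives spelled out.
3. In the add-on Statistics section, write that the upper 95% limit of 1 − NPV is 1.5% (NPV at least 98.5%), replace false positives with false negatives, and give the standard error as about 2.1% or less for rates up to 10%.
4. If the scan interval is to be examined, do so as a sensitivity analysis; the main estimate can keep all scans.

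The cost is wording only, with no change to enrolment, procedures or the 200 per group. The claim becomes more modest. Estimating the false negative rate itself would need a cohort enrolled regardless of ultrasound result, which is a different study.

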Staff at the academic unit of radiology will then have a telephone conversation with potential participants and ask them some screening questions. Eligible participants will be offered an appointment for an ultrasound and a MRI scan at the academic unit of radiology. Travel expenses for the participant and partner/friend/relative will be made available. When they attend the appointment informed consent will be taken. An important part of the consent procedure is the willingness of participants to allow their GP to be informed that they

are taking part in the study and have a copy of the Ultrasound and MRI reports (see safety section).

Women who are carrying a baby with a suspected non-brain abnormality will be given a supplementary information sheet which clearly states that scanning will be for the brain only. This is covered briefly in the main patient information sheet but we feel it important to emphasise this aspect of the study to this particular group of participants.

Study Visit (option 2 pathway)

Participants will attend a clinic at the academic unit of radiology. Informed consent will be taken.

After consent background information about the participant will be recorded by staff.

The participant will have a fetal brain ultrasound with a fetal medicine consultant. If the ultrasound shows normal brain development the participant will go on to have the MERIDIAN Add on study MRI scan. If the ultrasound detects a suspected brain abnormality the fetal medicine consultant will counsel the participant based on the anomaly seen and advise her to see her GP. The patient will have no further data collected for the MERIDIAN study. If it would be beneficial a clinical MRI will be offered to be done immediately during the same visit. This MRI will not be reported as part of the MERIDIAN Add on study.

The participant will then have the MRI scan and be offered an image of the baby to keep. Participants will also be offered a £10 voucher. Normally the participants will be able to have a discussion about the results of the scan and be given some immediate feedback, the participants will be reminded that results are going to be sent to their GP. No further patient contact is required after this visit.

Post Visit activities (option 2 pathway)

After the visit a copy of the scan reports will be sent to the participant's GP.

Safety

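### The shared eligibility footnote does not fit add-on study A2: option 1 rests a somatic abnormality on a normal scan, and reserve option 2 rests it on self-report

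*Protocol*

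**What the plan says.** All references are to the Protocol, Appendix, Add-on study.

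- **Inclusion Criteria.** A1 criterion 2: "Is thought to be carrying a fetus with no abnormality whatsoever (i.e. no brain or somatic abnormality". A2 criterion 2: "Is thought to be carrying a fetus with no brain abnormality but does have a confirmed somatic abnormality". Both carry the same double-asterisk footnote.
- **The footnote.** For the main route: "if recruited via option 1 this criterion will be based on a normal mid pregnancy anomaly scan in a fetal medicine centre". For the reserve route: "If recruited via option 2 this will be self-reported by the participant based on their medical care to date e.g. screening ultrasound".
- **Introduction.** For both studies, the women sought are those "whose fetus has had a detailed anomaly ultrasound by a feto-maternal expert which showed no brain abnormality".
- **Aims and Objectives.** A1 asks for the false negative rate of expert ultrasound for brain abnormalities. A2 asks for the rate of unexpected brain abnormalities in fetuses whose non-CNS abnormality is *known*.
- **Study Design.** Option 2 is a reserve, used only if option 1 recruits too few. Its pathway diagram begins: "Pregnant women whose pregnancy is normal are sought through".
- **Enrolment, option 2.** A supplementary sheet goes to a group described as: "Women who are carrying a baby with a suspected non-brain abnormality". The option 1 enrolment text also uses *suspected* for A2 women.
- **Study Visit and Post Visit activities.** Under option 2 a fetal medicine consultant scans the fetal brain, and only women with a normal result go on to the study MRI. A copy of the earlier anomaly scan report is requested under option 1. No such request appears under option 2.

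**The concern.** The two add-on studies are separated by one fact: whether the fetus has a somatic abnormality. The footnote fixes how that fact is established, and for A2 it does so badly on both routes.

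On option 1, the evidence for a somatic abnormality is a scan that must be normal. A site applying the rule as written could enter nobody into A2. A woman entered under the evident intent could later be called ineligible at consent, which the add-on lists as a ground for withdrawal.

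On option 2, the criterion asks for a *confirmed* abnormality and the aim for a *known* one, yet the footnote accepts what the woman reports. Nothing described on that route checks it, and there is no participant follow-up that might correct a wrong report. A2 could then count fetuses without a somatic abnormality, which would pull its rate towards the rate in unaffected fetuses.

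**Working it through.** **1. The plan's own figure.** Add-on Statistics gives an upper limit of 3/200 = 1.5% with no events in 200. This reproduces: 3/200 = 0.0150, and the exact one-sided 95% limit is 1 − 0.05^(1/200) = 0.0149. The limit depends only on the group size, so rewording the footnote does not change it.

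**2. The footnote against each criterion and route.**

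| Study and route | Criterion 2 needs | Footnote and pathway supply | Result |
|---|---|---|---|
| A1, option 1 | no brain or somatic abnormality | normal anomaly scan | consistent |
| A2, option 1 | normal brain, confirmed somatic abnormality | normal anomaly scan | contradictory |
| A1, option 2 | no brain or somatic abnormality | consultant brain ultrasound; somatic status self-reported | brain part secured, somatic part not |
| A2, option 2 | normal brain, confirmed somatic abnormality | consultant brain ultrasound; somatic status self-reported | brain part secured, somatic part not |

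**3. Dilution of the A2 rate.** The protocol gives none of the inputs, so all are assumptions. Let s be the share of A2 entering by option 2, m the share of those with no real somatic abnormality, and r the brain-finding rate in true A2 fetuses. Take the rate in misassigned fetuses as about 0, the worst case for dilution. The observed rate is then r × (1 − s × m). With r = 5%:

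| s | s × m for m = 10% to 30% | Observed rate |
|---|---|---|
| 10% | 1% to 3% | 4.95% to 4.85% |
| 20% | 2% to 6% | 4.9% to 4.7% |
| 50% | 5% to 15% | 4.75% to 4.25% |

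The relative loss is s × m whatever r is. At s = 20% and m = 30% it is 6%: r = 3% reads 2.82%, and r = 10% reads 9.4%.

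For scale, the standard error at p = 5% and n = 200 is √(0.05 × 0.95/200) = 1.54 percentage points. The losses in the 10% and 20% rows, 0.05 to 0.3 points, are small beside it. Those in the 50% row reach 0.75 points, about half of it.

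**The case against.** The strongest reply is that the intent is plain. The introduction describes a detailed expert scan showing no brain abnormality, so *normal* in the footnote must mean a normal brain. Option 2 is a reserve that may never open. *Suspected* describes who receives an information sheet and is not an eligibility rule. A woman found to be ineligible can be withdrawn.

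Most of this stands, and it limits the point. It does not remove it. The footnote is the operative rule and should be one that A2 women can meet. Withdrawal for ineligibility helps only if someone learns that the report was wrong, and option 2 describes no step that would show it.

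A reader might also infer three stronger claims that the documents do not support:

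- **That A1 enrols outside its aim.** The aim concerns brain abnormalities missed by expert ultrasound, and under option 2 the consultant's brain scan comes before the MRI. A brain abnormality missed there and seen on MRI is a genuine event for A1, whatever the somatic status. Only the somatic half of A1's written criterion rests on self-report.
- **That option 1 accepts a scan by anyone in a fetal medicine centre, so A1 evaluates a different test.** The introduction requires a feto-maternal expert. The option 2 enrolment text describes its wider group as women not scanned by a fetal medicine consultant, which implies that option 1 women were.
- **That the word *normal* lets wrong fetuses into A2.** Read literally it admits none; it does not admit the wrong ones.

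**Conclusion.** The point holds for A2. Under option 1 the footnote contradicts the criterion it is meant to explain: a drafting error, with the intended meaning recoverable from the introduction and no bias following from it. Under option 2 there is a substantive gap, because A2 can count fetuses whose non-CNS abnormality is neither confirmed nor known. For A1 the gap is confined to the somatic half of the criterion and leaves its aim intact.

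The size cannot be fixed from the protocol. It would be tempting to apply a self-report error rate to all 200 fetuses, but only option 2 entrants can be affected, and their share is not stated. With a modest share the dilution is a few tenths of a percentage point at most on an assumed 5% rate. The planned 200 per group and the 1.5% limit are unaffected, and so is MERIDIAN's primary analysis. The reason to act is that the rule is wrong as written and cheap to correct.

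**What to change.** Replace the shared footnote with separate wording by study and by brain and somatic status:

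- **A1, option 1:** detailed scan by a feto-maternal expert showing no brain or somatic abnormality.
- **A2, option 1:** detailed scan by a feto-maternal expert showing no brain abnormality, with the somatic abnormality documented.
- **Option 2:** brain status from the study's consultant ultrasound; somatic status from a written scan report or maternity record. Alternatively, restrict option 2 to A1.

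Reconcile *confirmed*, *known* and *suspected*, and the option 2 diagram's restriction to normal pregnancies, across the aims, criteria and both enrolment sections. State that a woman whose report does not document a somatic abnormality is left out of the A2 estimate.

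The cost is protocol wording, plus extending to option 2 the report request that option 1 already has. The downside is that a few option 2 women without a report cannot be counted. If they are replaced, 200 and 1.5% stand. If 4 to 12 were lost from a group without replacement (2–6% of 200, the 20% row above), the zero-event limit would be 3/196 = 1.53% to 3/188 = 1.60%.
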